Revlimid® (lenalidomide) is indicated for the treatment of patients with transfusion-dependent anemia due to low- or intermediate-1-risk myelodysplastic syndromes associated with a deletion 5q cytogenetic abnormality with or without additional cytogenetic abnormalities. Revlimid® is also approved in combination with dexamethasone for the treatment of patients with multiple myeloma that have received at least one prior therapy. All other uses are considered investigational.

3.4.2 EVEROLIMUS INDICATIONS AND USAGE:

AFINITOR® (everolimus) is indicated for the treatment of patients with advanced renal cell carcinoma after failure of treatment with sunitinib or sorafenib. The recommended dose of AFINITOR for treatment of advanced renal cell carcinoma is 10 mg, to be taken once daily at the same time every day, either with or without food. AFINITOR tablets should be swallowed whole with a glass of water. The tablets should not be chewed or crushed. Continue treatment as long as clinical benefit is observed or until unacceptable toxicity occurs.

3.5 Adverse Events

3.3.1 Lenalidomide

Most frequently reported adverse events reported during clinical studies with lenalidomide in oncologic and non-oncologic indications, regardless of presumed relationship to study medication include: anemia, neutropenia, thrombocytopenia and pancytopenia, abdominal pain, nausea, vomiting and diarrhea, dehydration, rash, itching, infections, sepsis, pneumonia, UTI, Upper respiratory infection, cellulites, atrial fibrillation, congestive heart failure, myocardial infarction, chest pain, weakness, hypotension, hypercalcemia, hyperglycemia, back pain, bone pain, generalized pain, dizziness, mental status changes, syncope, renal failure, dyspnea, pleural effusion, pulmonary embolism, deep vein thrombosis, CVA, convulsions, dizziness, spinal cord compression, syncope, disease progression, death not specified and fractures.

Complete and updated adverse events are available in the Investigational Drug Brochure and the IND Safety Letters.

3.3.2 Everolimus

The data described below reflect exposure to AFINITOR (n=274) and placebo (n=137) in a randomized, controlled trial in patients with metastatic renal cell carcinoma who received prior treatment with sunitinib and/or sorafenib. The median age of patients was 61 years (range 27-85), 88% were Caucasian, and 78% were male. The median duration of blinded study treatment was 141 days (range 19-451) for patients receiving AFINITOR and 60 days (range 21-295) for those receiving placebo. The most common adverse reactions (incidence $\geq 30\%$) were stomatitis, infections, asthenia, fatigue, cough, and diarrhea. The most common grade 3/4 adverse reactions (incidence $\geq 3\%$) were infections, dyspnea, fatigue, stomatitis, dehydration, pneumonitis, abdominal pain, and asthenia. The most common laboratory abnormalities (incidence $\geq 50\%$) were anemia, hypercholesterolemia, hypertriglyceridemia, hyperglycemia, lymphopenia, and increased creatinine. The most common grade 3/4 laboratory abnormalities (incidence $\geq 3\%$) were lymphopenia, hyperglycemia, anemia, hypophosphatemia, and hypercholesterolemia. Deaths due to acute respiratory failure (0.7%), infection (0.7%) and acute renal failure (0.4%) were observed on the AFINITOR arm but none on the placebo arm. The rates of treatment-emergent adverse events (irrespective of causality) resulting in permanent discontinuation were 14% and 3% for the AFINITOR and placebo treatment groups, respectively. The most common adverse reactions (irrespective of causality) leading to treatment discontinuation were pneumonitis and dyspnea. Infections, stomatitis, and pneumonitis were the most common reasons for treatment delay or dose reduction. The most common medical interventions required during AFINITOR treatment were for infections, anemia, and stomatitis.

4 Study Objectives and Endpoints

4.1 Objectives

4.1.1 Primary objectives

- Determine the maximum tolerated dose (MTD) and define the phase II recommended dose (P2RD) for the combination of lenalidomide and everolimus in patients with advanced solid malignancies
- Assess the safety and tolerability of the combination of everolimus and lenalidomide in patients with advanced solid malignancies

4.1.2 Secondary study objectives

- Assess for drug-drug interaction through pharmacokinetic analysis for everolimus and lenalidomide
- Identify preliminary evidence of efficacy by assessing the clinical benefit rate (CR+PR+SD) achieved in an expanded cohort of renal cell carcinoma patients
- Assess preliminary efficacy in an expanded cohort of patients with adenoid cystic carcinoma

4.1.3 Correlative Objectives

- Correlate mTOR pathway protein expression in archival diagnostic tumor tissue with the clinical activity of everolimus
- Determine the predictive ability of changes in inflammatory and immunologic markers in paired blood samples as pharmacodynamic evidence of target modulation by escalating doses of lenalidomide
- Correlate changes in level of cathepsin G in plasma with escalating doses of lenalidomide and with incidence of venous thromboembolism
- Correlate myb protein expression with the efficacy of the combination of everolimus and lenalidomide in patients with adenoidcystic carcinoma.
- Assess the predictive value of myb gene alteration in patients with adenoidcystic cancer

4.2 Endpoints

4.2.1 Primary Endpoint

Maximum tolerated dose (MTD) of the combination of lenalidomide and everolimus

Safety will be assessed according to NCI CTCAE 4.0 (Appendix C)

Assessment of DLT will be performed during the first cycle only and the following will constitute DLT in this study:

- Grade 4 hematologic toxicity lasting more than 7 days
- Grade 4 Neutropenia of any duration with fever $\geq 38.5^{\circ}\text{C}$
- Grade ≥ 3 nausea and or vomiting in spite of standard supportive therapy
- Grade ≥ 3 non-hematologic toxicity (exclude alopecia)
- Inability to re-treat patient within 2 wks of scheduled treatment due to treatment-related toxicity
- Inability to deliver all doses of Everolimus during the first cycle due to an unexpected drug-related toxicity (if everolimus related toxicity is an expected toxicity as per current package insert, then it will not be considered a DLT). These subjects should be discontinued from the study.
- Discontinuation of the study prior to completing the entire first treatment cycle for reasons other than DLT, a subject will be added to that dose-level cohort.
- The occurrence of one of the above drug-related toxicities will result in a clinical and/or laboratory assessment to be performed within 7 days following the initial finding to examine the subject for resolution of the toxicity. Lack of resolution of any of these toxicities according to the guidelines above will be considered a DLT and result in discontinuation of that subject

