5.1 Overall design

This is a phase I, open-label, single institution, non-randomized study of escalating doses of daily, orally administered lenalidomide in combination with standard doses of everolimus, an orally available mTOR inhibitor. The trial is open to patients with advanced solid malignancies who have failed or are intolerant of available standard treatment options for their disease. Dose escalation will proceed in a modified Fibonacci 3+3 fashion with the requirement that dose escalation to the next level can only proceed if 0 of 3 or ≤ 1 of 6 patients experience a dose limiting toxicity (DLT). Four escalating dose cohorts and three deescalating dose cohorts will be used to evaluate different doses of lenalidomide and everolimus starting with the approved and or clinically relevant doses of both agents. The proposed starting dose level 1 is 10mg of lenalidomide (days 1 – 28) in combination with 10mg of everolimus (days 1 - 28) in a 28-day cycle. A serial de-escalation to 10mg of lenalidomide (days 1-21 of a 28 day cycle) and 5mg of everolimus will be carried out if DLT is observed in $\geq 33\%$ of patients enrolled to the starting dose cohort. The MTD is the highest dose level of lenalidomide and everolimus (up to a maximum dose of 25mg and 10mg respectively) at which $<33\%$ of the dose cohort experiences DLT after 1 cycle (28 days) of therapy. The established MTD will be the recommended dose for follow-up phase II study. To obtain preliminary clinical benefit of this combination, an expanded cohort of 15 patients with clear cell renal cell carcinoma, adenoidcystic carcinoma and neuroendocrine tumors will be treated at the define MTD. To allow for assessment of drug-drug interaction using PK analysis, lenalidomide will be administered alone on day 1 of the first cycle followed by both agents on day 2 cycle 1. Both drugs will be started simultaneously on day 1 of all subsequent cycles.

In addition, a parallel cohort of 9 additional patients with adenoicystic cancer will be treated at the RP2D. This is to enable us to obtain further evidence in support of the efficacy of this regimen in patients with adenoicystic cancer as observed in the limited number of patients with this cancer type who were enrolled in the escalation phase of the study.

Table 1

Dose Level	Lenalidomide (day 1 to 28)	Everolimus (day 1-28)	Patient Enrolment	Remarks
-2	10mg Days 1-21	5mg every other day	3 + 3	If DLT, study will close without defining a MTD

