A phase I study in subjects with refractory or relapsed multiple myeloma was conducted to identify the maximum tolerated dose (MTD) and to evaluate the safety of lenalidomide given orally for up to 4 weeks at 5 mg/day, 10 mg/day, 25 mg/day and 50 mg/day. Secondary objectives included evaluation of response to lenalidomide, as well as pharmacokinetics and identification of surrogate markers to aid in defining mechanisms of action. Subjects who tolerated study drug with acceptable toxicity and were without disease progression were permitted to continue on therapy beyond 28 days as part of an extension phase for over 1 year. Twenty-seven subjects were enrolled, of whom 15 had undergone prior autologous stem cell transplantation and 16 had received prior thalidomide, with a median of 3 prior regimens (range 2-6). All subjects had relapsed MM and 18 (72%) were refractory to salvage therapy. Two subjects were removed from study on the first day of treatment due to rapid disease progression, which resulted in renal dysfunction and rendered them ineligible. The first group of 3 subjects were treated for 28 d at 5 mg/d without any dose limiting toxicity (DLT). The second cohort of 3 subjects commenced therapy at 10 mg/day. In one subject, DLT was encountered with grade 2 fever as well as grade 3 leukopenia and neutropenia, resulting in removal from study before day 28. Two subjects tolerated drug. Three additional subjects were treated at 10 mg/day with no attributable toxicity within the first 28 days. In the third cohort of 3 subjects at 25mg/day, drug was well tolerated within the first 28 days but grade 3 thrombocytopenia and grade 3 and 4 neutropenia occurred during the second month, resulting in 2 subjects being removed from study. In the fourth cohort at 50mg/day, the first 3 subjects tolerated treatment without DLT in the first 28 days and a subsequent 10 subjects also tolerated drug without DLT within the first 28 days. However, subsequent grade 3 thrombocytopenia and grade 3/4 neutropenia in the extension phase has prompted dose reduction and GCSF support in all subjects. No significant somnolence, constipation or neuropathy has been seen in any cohort. Median duration of therapy is currently 4 months [range 2 weeks – 14 months] and 11 subjects continue on treatment. Maximal protein reductions seen during therapy in subjects who have received ≥ 28 d of treatment are summarized below:

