Table 2: Monoclonal protein reductions in a phase I study with lenalidomide

dose	pts [n]	< 25%	$\geq 25%$ <50%	>50%	Progression
5	3	-	2	1	-
10	5	-	-	1	4
25	3	1	2	-	-
50	13	3	5	4	1
Subtotals	24	4 (17%)	9 (37%)	6 (25%)	5 (21%)

Thus, best responses in protein of $\geq 25\%$ have been seen in 15 of 24 evaluable pts (63%), and a $<25\%$ reduction has been seen in 4 subjects to achieve stable disease or better in 19 of 24 (79%). Pharmacokinetics [days 1-4, and 28] have been completed in 24 subjects and reveal rapid absorption (t max: 1-1.5 h); monophasic elimination (t $\frac{1}{2}$: 3.1-4.2 h), and low to moderate inter-subject variability for AUC (11-52%) and Cmax (3-33%). Furthermore, there was no significant accumulation by day 28. In conclusion, these studies suggest lenalidomide at the dose levels

studied has anti-tumor activity, Continuous pharmacokinetics with convenient daily oral dosing and acceptable toxicity in subjects with relapsed and refractory multiple myeloma. Given the myelosuppression beyond day 28 seen in all subjects at 50 mg/day, this dose was considered to be the DLT, and thus the 25 mg/day dose level as a continuous daily schedule of administration was considered MTD. Given the activity of the drug seen at lower dose levels and the PK characteristics observed, 30 mg/day in divided or single daily dose was assessed for activity and safety, and to determine whether a divided dose schedule is superior. In addition, a 3-week on and one-week off schedule was assessed to determine if a cycling schedule would decrease the myelosuppression that was observed in earlier trials with daily dosing. In this phase II study, 70 subjects with relapsed and refractory myeloma were enrolled at several centers in the U.S. Richardson et al reported that 26% of subjects required dose reduction due to myelosuppression in this study. Responses that were observed included 4% of subjects with complete responses, 17% with partial responses and 33% with minimal responses. Progressive disease occurred in 15% of subjects.¹⁷ It was concluded that daily dosing was better tolerated than twice daily dosing because of a lower incidence and severity of myelosuppression.

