Discrete, reversible changes in liver enzymes have been found to occur in numerous patients during treatment with RAD001 in oncology clinical studies, and in a study in rheumatoid arthritis. In oncology studies, these changes may be evident only in patients without severe underlying morbidity. The increase in transaminase's (AST and ALT) generally appears after 4 weeks of treatment. In all but a few cases it does not exceed Grade 1 ($\leq 2.5 \times \text{ULN}$). Similarly, mild increases in alkaline phosphatases can coexist. Spontaneous corrections or intermittent correction with continued treatment can occur. Serum bilirubin is not increased. In studies of patients with advanced cancers, clinically relevant changes in liver enzymes have been invariably associated with the presence of liver metastases and/or progression of the underlying cancer.

Renal failure has been reported in five suspected cases to date. One patient with no alternative explanation made a complete recovery following study drug adjustment and no treatment/therapy for the event. The rest of the patients had concurrent morbidities, which might have contributed to the reported events.

Hypophosphatemia, hypomagnesemia, hyponatremia and hypocalcemia have been reported as serious adverse reactions. Electrolytes should be monitored in patients treated with RAD001.

Table 6 provides general recommendations for the management of patients, with suspected drug toxicities while on treatment with RAD001 as single-agent therapy.

More detailed information regarding RAD001 reported suspected toxicities and individual cases is provided in the [Investigator's Brochure].

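### The recommended phase II dose is taken automatically from cycle 1 DLTs, with no rule for weighing later toxicity, although the protocol's own lenalidomide data describe limiting myelosuppression after day 28

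*Combined protocol and SAP*

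**What the plan says.** The plan fixes the dose in three linked steps.

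- **Window (Section 4.2.1 and synopsis).** "Assessment of DLT will be performed during the first cycle only".
- **MTD (Section 5.1 and synopsis).** The MTD is the highest level at which fewer than 33% "of the dose cohort experiences DLT after 1 cycle (28 days) of therapy", with lenalidomide and everolimus limited "up to a maximum dose of 25mg and 10mg respectively". Under the 3+3 rule, "dose escalation to the next level can only proceed if 0 of 3 or" at most 1 of 6 patients have a DLT.
- **RP2D (Section 5.1 and synopsis).** "The established MTD will be the recommended dose for follow-up phase II study". No other input is named.

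Sections 5.7.1 and 5.7.3 deal with toxicity after cycle 1 through individual dose changes and leave cohort decisions to Table 1.

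Section 5.2.2 summarises a phase I study of daily single-agent lenalidomide in multiple myeloma. At 50 mg/day, after the first three subjects had no DLT, a "subsequent 10 subjects also tolerated drug without DLT within the first 28 days". The summary then concludes: "Given the myelosuppression beyond day 28 seen in all subjects at 50 mg/day, this dose was considered to be the DLT". The same sentence goes on to name 25 mg/day, given continuously, as that study's MTD.

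**The concern.** The primary objectives in Section 4.1.1 are the MTD, the RP2D and the tolerability of a regimen that Section 5.11 continues until progression or intolerance. The RP2D nevertheless rests on 28 days of observation. For one of the two drugs, on the same continuous daily schedule, the protocol reports a study in which the toxicity that decided the MTD came after day 28.

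As written, the trial can name an RP2D without weighing later-cycle tolerability, even when its own patients have shown it to be poor. A follow-on phase II trial would then inherit that dose.

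**Working it through.** **1. The plan's own counts.** Section 10.6 gives up to 30 escalation patients (5 levels × 6 = 30), or 15 if there are no DLTs (5 × 3 = 15). Both reproduce. It also says that 21 patients were needed for escalation, and 21 + 15 + 9 = 45 matches the stated total. So 15 + 9 = 24 patients are treated after escalation. Their later cycles give information on tolerability, but the plan gives that information no role in naming the RP2D.

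**2. The cited study's counts (Section 5.2.2).** 27 enrolled − 2 removed on day one = 25. By dose (5, 10, 25, 50 mg): 3 + 6 + 3 + 13 = 25. Table 2, restricted to subjects with at least 28 days of treatment, has 3 + 5 + 3 + 13 = 24; the one missing at 10 mg matches the subject removed before day 28. The counts are consistent.

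**3. First 28 days against later, by dose.** Intervals are 95% Clopper-Pearson.

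| Daily dose | First 28 days | After day 28 |
|---|---|---|
| 10 mg | 1 of 6 with a DLT | not described |
| 25 mg | well tolerated, read here as 0 of 3 (0% to 71%) | 2 of 3 removed in month 2 (9% to 99%) |
| 50 mg | 0 of 3 + 10 = 13 (upper limit 1 − 0.025^(1/13) = 24.7%) | reduction and G-CSF in all 13 (lower limit 0.025^(1/13) = 75.3%) |

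On these counts, a rule that passes a level at 0 of 3 in 28 days would have passed 50 mg, the dose that the cited study rejected on later events. This uses the cited study's own DLT calls; the protocol does not give that study's DLT definition.

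**4. How far this trial's definition reaches past day 28.** One criterion does: inability to re-treat within 2 weeks. That extends to about day 28 + 14 = 42, but only for toxicity that blocks the start of cycle 2. Cytopenia that begins during cycle 2 is outside it.

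**5. Would a longer window be enough?** The month-2 events at 25 mg were grade 3 thrombocytopenia and grade 3 and 4 neutropenia. Under Section 4.2.1, a haematologic DLT must be grade 4 lasting more than 7 days, or grade 4 neutropenia with fever. Grade 3 cytopenias, and shorter afebrile grade 4 neutropenia, do not meet those criteria in any cycle. Counting only DLTs over more cycles could therefore miss the events reported.

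**6. Where later information goes.** Section 10.2 summarises doses and cycles delivered by dose level. Section 10.4 summarises adverse events and discontinuations by dose level. Sections 9.3 and 10.5 provide ongoing safety review. None of these sections says that the findings may change the RP2D.

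**The case against.** A first-cycle DLT window is a common phase I choice, and the plan is not silent on later toxicity. The re-treatment criterion covers delayed recovery, the expansion is meant to characterise safety further, adverse events are summarised without a cycle limit, and the monitoring committee may stop the study. The cited study, knowing the month-2 events, still named 25 mg daily as its MTD. That is this trial's lenalidomide cap, so single-agent late toxicity is already partly reflected in the ceiling.

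Most of this stands, and it narrows the point. What it does not supply is any route from later-cycle findings to the RP2D, or any information on the combination, for which the documents give no late-toxicity rates.

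A reader might infer more than the documents support:

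- **That a 28-day window fails for this drug in general.** One of 6 subjects at 10 mg had a DLT with grade 3 leukopenia and neutropenia before day 28, so the myelosuppression is not always late.
- **That pooling 25 and 50 mg strengthens the case.** 50 mg is above the cap, which leaves 3 subjects at a dose this trial can reach.
- **That everolimus adds a second late toxicity.** Section 5.7.5 says the transaminase rise "generally appears after 4 weeks of treatment", but adds that it seldom exceeds grade 1 and may correct on treatment. That is not evidence of late dose-limiting toxicity.
- **That escalation should have used two cycles.** Pass probabilities under such a window would rest on assumed rates, and escalation is already complete.

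**Conclusion.** The point holds as a gap in how the RP2D is named. The plan equates it with a 28-day MTD, while the protocol itself describes a study of one component in which myelosuppression after day 28 decided the MTD. Under the stated rule, later-cycle tolerability in this trial's patients cannot alter the RP2D.

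The size of the risk for the combination is unknown. The evidence at a reachable dose is 2 of 3 subjects, in single-agent use in myeloma. It shows that late limiting toxicity can occur on this schedule. It does not show that 25 mg, or any level in Table 1, is intolerable here, and it does not invalidate the escalation decisions already made. The stated sample sizes are not in dispute.

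**What to change.** Keep the cycle 1 DLT rule for escalation. In the synopsis and Section 5.1, replace the sentence that makes the MTD the recommended dose with wording to this effect:

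> The RP2D will be selected at or below the MTD after a documented review of cumulative tolerability over all available cycles in escalation and expansion patients. The review will cover grade 3-4 haematologic and other toxicity; reductions, interruptions and discontinuations for toxicity; and delivered dose intensity of each drug.

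Section 5.1 also treats the nine adenoid cystic patients at the RP2D. If their data feed the review, call that dose provisional until the review is done.

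In Section 10.4, tabulate first-cycle and cumulative rates side by side by dose level, with the number of patients evaluable in each cycle.

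Do not attach a 33% trigger to cycle 2. With three patients at a level, one event is 1/3 = 33.3% and would trip it. At assumed later-event rates of 10%, 20% and 30%, at least one event in three occurs with probability 1 − 0.9³ = 27%, 1 − 0.8³ = 49% and 1 − 0.7³ = 66%. If the trigger counted only DLT-type events, it would also miss the grade 3 cytopenias.

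**Cost.** One paragraph and one table, from adverse-event, dosing and diary records already collected. The RP2D waits for later-cycle data; Section 9.1 already allows 3 months from last expansion enrolment, about three 28-day cycles. The RP2D may fall below the cycle 1 MTD.
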